## COLLECTION OF PREGNANCY INFORMATION

### Male participants with partners who become pregnant

- The Investigator will attempt to collect pregnancy information on any male participant's female partner who becomes pregnant while the male participant is in this study. This applies only to male participants who receive study treatment.
- After obtaining the necessary signed informed consent from the pregnant female partner directly, the Investigator will record pregnancy information on the appropriate form and submit it to the Sponsor within 24 hours of learning of the partner's pregnancy. The female partner will also be followed to determine the outcome of the pregnancy. Information on the status of the mother and child will be forwarded to the Sponsor. Generally, the follow-up will be no longer than 1 year following the estimated delivery date. Any termination of the pregnancy will be reported regardless of fetal status (presence or absence of anomalies) or indication for procedure.

### Female participants who become pregnant

- The Investigator will collect pregnancy information on any female participant who becomes pregnant while participating in this study. Information will be recorded on the appropriate form and submitted to the Sponsor within 24 hours of learning of a participant's pregnancy. The participant will be followed to determine the outcome of the pregnancy. The Investigator will collect follow-up information on the participant and the neonate, and the information will be forwarded to the Sponsor. Generally, follow-up will not be required for longer than 1 year beyond the estimated delivery date. Any termination of pregnancy will be reported, regardless of fetal status (presence or absence of anomalies) or indication for procedure.

Any pregnancy complication or elective termination of a pregnancy will be reported as an AE or SAE. A spontaneous abortion is always considered to be an SAE and will be reported as such. Any poststudy pregnancy-related SAE considered reasonably related to the study treatment by the Investigator will be reported to the Sponsor as described in [Section 10.4.1.2](#). While the Investigator is not obligated to actively seek this information in former study participants, he or she may learn of an SAE through spontaneous reporting.

- The Investigator must immediately discontinue study treatment for any female participant who becomes pregnant while participating in the study.

## Appendix B Definition of urgent heart failure visit

An urgent HF Visit is defined as an event that meets all of the following (in accordance with the 2014 Key Data Elements and Definitions for Cardiovascular Endpoint Events in Clinical Trials guidance document [54]):

1. The patient has an urgent, unscheduled office/practice or ED visit for a primary diagnosis of HF, but not meeting the criteria for a HF hospitalization
2. The following signs and symptoms for HF hospitalization (ie, symptoms, physical examination findings/laboratory evidence of new or worsening HF) must be met:

*The patient exhibits documented new or worsening symptoms due to HF on presentation, including at least ONE of the following symptoms:*

- A) Dyspnea (dyspnea with exertion, dyspnea at rest, orthopnea, paroxysmal nocturnal dyspnea)
- B) Decreased exercise tolerance
- C) Fatigue
- D) Other symptoms of worsened end-organ perfusion or volume overload (must be specified and described by the protocol)

*The patient has objective evidence of new or worsening HF, consisting of at least TWO physical examination findings OR one physical examination finding and at least ONE laboratory criterion), including:*

- A) Physical examination findings considered to be due to heart failure, including new or worsened:
  - a) Peripheral edema
  - b) Increasing abdominal distention or ascites (in the absence of primary hepatic disease)
  - c) Pulmonary rales/crackles/crepitations
  - d) Increased jugular venous pressure and/or hepatjugular reflux
  - e) S3 gallop
  - f) Clinically significant or rapid weight gain thought to be related to fluid retention
- B) Laboratory evidence of new or worsening HF, if obtained within 24 hours of presentation, including:
  - a) Increased B-type natriuretic peptide (BNP)/ N-terminal pro-BNP (NT-proBNP) concentrations consistent with decompensation of heart failure (such as BNP >500 pg/mL or NT-proBNP >2000 pg/mL). In patients with chronically elevated natriuretic peptides, a significant increase should be noted above Baseline.
  - b) Radiological evidence of pulmonary congestion

- c) Non-invasive diagnostic evidence of clinically significant elevated left- or right-sided ventricular filling pressure or low cardiac output. For example, echocardiographic criteria could include:  $E/e' > 15$  or D-dominant pulmonary venous inflow pattern, plethoric inferior vena cava with minimal collapse on inspiration, or decreased left ventricular outflow tract (LVOT) minute stroke distance (time velocity integral [TVI])

OR

- d) Invasive diagnostic evidence with right heart catheterization showing a pulmonary capillary wedge pressure (pulmonary artery occlusion pressure)  $\geq 18$  mmHg, central venous pressure  $\geq 12$  mmHg, or a cardiac index  $< 2.2$  L/min/m^2
3. The patient receives initiation or intensification of treatment specifically for HF, including at least one of the following (**NOTE**: augmentation of oral diuretic therapy will not be considered sufficient):
- A) Intravenous diuretic or vasoactive agent (eg, inotrope, vasopressor, or vasodilator)
  - B) Mechanical or surgical intervention, including:
    - a) Mechanical circulatory support (eg, intra-aortic balloon pump, ventricular assist device, extracorporeal membrane oxygenation, total artificial heart)
    - b) Mechanical fluid removal (eg, ultrafiltration, hemofiltration, dialysis)

## Appendix C Kansas City Cardiomyopathy Questionnaire-12

### Kansas City Cardiomyopathy Questionnaire (KCCQ-12)

The following questions refer to your heart failure and how it may affect your life. Please read and complete the following questions. There are no right or wrong answers. Please mark the answer that best applies to you.

1. Heart failure affects different people in different ways. Some feel shortness of breath while others feel fatigue. Please indicate how much you are limited by heart failure (shortness of breath or fatigue) in your ability to do the following activities over the past 2 weeks.

| Activity                                      | Extremely Limited     | Quite a bit Limited   | Moderately Limited    | Slightly Limited      | Not at all Limited    | Limited for other reasons or did not do the activity |
|---|-----------------------|-----------------------|-----------------------|-----------------------|-----------------------|--|
| a. Showering/bathing                          |  |  |  |  |  |                                 |
| b. Walking 1 block on level ground            |  |  |  |  |  |                                 |
| c. Hurrying or jogging (as if to catch a bus) |  |  |  |  |  |                                 |
|   | 1                     | 2                     | 3                     | 4                     | 5                     | 6  |

2. Over the past 2 weeks, how many times did you have swelling in your feet, ankles or legs when you woke up in the morning?

| Every morning         | 3 or more times per week but not every day | 1-2 times per week    | Less than once a week | Never over the past 2 weeks |
|-----------------------|--|-----------------------|-----------------------|-----------------------------|
|  |                       |  |  |        |
| 1                     | 2  | 3                     | 4                     | 5                           |

3. Over the past 2 weeks, on average, how many times has fatigue limited your ability to do what you wanted?

| All of the time       | Several times per day | At least once a day   | 3 or more times per week but not every day | 1-2 times per week    | Less than once a week | Never over the past 2 weeks |
|-----------------------|-----------------------|-----------------------|--|-----------------------|-----------------------|-----------------------------|
|  |  |  |                       |  |  |        |
| 1                     | 2                     | 3                     | 4  | 5                     | 6                     | 7                           |

4. Over the past 2 weeks, on average, how many times has shortness of breath limited your ability to do what you wanted?

| All of the time       | Several times per day | At least once a day   | 3 or more times per week but not every day | 1-2 times per week    | Less than once a week | Never over the past 2 weeks |
|-----------------------|-----------------------|-----------------------|--|-----------------------|-----------------------|-----------------------------|
|  |  |  |                       |  |  |        |
| 1                     | 2                     | 3                     | 4  | 5                     | 6                     | 7                           |

5. Over the past 2 weeks, on average, how many times have you been forced to sleep sitting up in a chair or with at least 3 pillows to prop you up because of shortness of breath?

| Every night           | 3 or more times per week but not every day | 1-2 times per week    | Less than once a week | Never over the past 2 weeks |
|-----------------------|--|-----------------------|-----------------------|-----------------------------|
|  |                       |  |  |        |
| 1                     | 2  | 3                     | 4                     | 5                           |

Rev. 2012-04-11

6. Over the past 2 weeks, how much has your heart failure limited your enjoyment of life?

|  |  |   |  |   |
|--|--|---|--|---|
| It has extremely
limited my enjoyment
of life | It has limited my
enjoyment of life
quite a bit | It has moderately
limited my enjoyment
of life | It has slightly limited
my enjoyment of life | It has not limited
my enjoyment
of life at all |
|                                       |   |                                        |                                   |                                        |
| 1  | 2  | 3   | 4  | 5   |

7. If you had to spend the rest of your life with your heart failure the way it is right now, how would you feel about this?

[figure not shown]
|                         |                        |                       |                       |                         |
|-------------------------|------------------------|-----------------------|-----------------------|-------------------------|
| Not at all
satisfied | Mostly
dissatisfied | Somewhat
satisfied | Mostly
satisfied   | Completely
satisfied |
|    |   |  |  |    |
| 1                       | 2                      | 3                     | 4                     | 5                       |

8. How much does your heart failure affect your lifestyle? Please indicate how your heart failure may have limited your participation in the following activities over the past 2 weeks.

| Activity                                | Severely
Limited   | Limited
quite a bit | Moderately
limited | Slightly
limited   | Did not
limit at all | Does not apply
or did not do for
other reasons |
|--|-----------------------|------------------------|-----------------------|-----------------------|-------------------------|--|
| a. Hobbies, recreational activities            |  |   |  |  |    |                                 |
| b. Working or doing household chores           |  |   |  |  |    |                                 |
| c. Visiting family or friends out of your home |  |   |  |  |    |                                 |
|  | 1                     | 2                      | 3                     | 4                     | 5                       | 6  |

## Appendix D General guidance for the follow-up of laboratory abnormalities by Sanofi

[figure not shown]

**Note:**

- The procedures described in the above flowchart are to be discussed with the patient only in case the event occurs. If applicable (according to local regulations), an additional consent (e.g., for HIV testing) will only be obtained in the case the event actually occurs.
- For individuals of African descent, the relevant value of concern is <math><1000/\text{mm}^3</math>

Neutropenia is to be recorded as an AE only if at least 1 of the criteria listed in the general guidelines for reporting adverse events in [Section 10.4.3](#) is met.

### THROMBOCYTOPENIA

[figure not shown]

**Note:**

[figure not shown]
The procedures above flowchart are to be discussed with the patient only in case described in the the event occurs. If applicable (according to local regulations), an additional consent (e.g., for HIV testing) will only be obtained in the case the event actually occurs.

Thrombocytopenia is to be recorded as an AE only if at least 1 of the criteria listed in the general guidelines for reporting adverse events in [Section 10.4.3](#) is met.

### INCREASE IN ALT

### INCREASE IN CPK SUSPECTED TO BE OF NON-CARDIAC ORIGIN AND NOT RELATED TO INTENSIVE PHYSICAL ACTIVITY

Increase in CPK is to be recorded as an AE only if at least 1 of the criteria in the general guidelines for reporting adverse events in [Section 10.4.3](#) is met.

## Appendix E Guidance for the follow-up of acute worsening of renal function

### Rapid change in renal function of greater than **30%** as compared with the **mean of the prior 2 study visits**

- Evaluate if the patient is taking medications which alter serum creatinine such as: trimethoprim, fenofibrate, non-steroidal anti-inflammatory agents, cimetidine, cephalosporins, probenecid, aminoglycosides, amphotericin, ketoconazole, clofibrate, contrast agents
- Evaluate if any of the following conditions are present that may alter serum creatinine:
  - Significant increase or decrease in blood pressure due to changes in antihypertensive therapy or diuretic treatment
  - Plasma volume depletion or expansion
  - Flu-like symptoms
  - Infected urine
  - Obstructive uropathy
  - New onset or exacerbation of heart failure
- If any of the above conditions are met, the Investigator should take corrective measures to resolve and schedule an interim visit to evaluate the serum creatinine/GFR and the patient's clinical status 1 week from the institution of corrective measures. Patients with a suspected renal event (reduction of eGFR) should have a repeat assessment of renal function 30 to 45 days following the onset of the event to confirm it is sustained (this repeat renal assessment may occur beyond the last planned visit per protocol). If acute renal failure is suspected, further clinical evaluation should be performed as per local standard of care, including confirmation of renal laboratory parameters, and consideration should be given to a nephrology referral.
- Permanent discontinuation of IMP should be a last resort, and if IMP needs to be withheld, it should be done so temporarily when possible. Permanent discontinuation of IMP is required if eGFR <15 mL/min/1.73 m^2 that has been confirmed on repeated testing and in the absence of a reversible cause (see protocol [Section 10.3.3](#)).

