| Day (window in days)                                    | within 14 days before randomization  | 1  | 8 (±3) | 15 (±3)      | 29 (±3) | 113 (±7) | (±7)                             | (±7)   |                      |   | (±4)                         |
| Laboratory testing i                         |                                      |  |        |              |         |          |                                  |  |                      |   |                              |
| BNP and NT-proBNP (including at discharge) j | X                                    | X  |        |              | X       | X        | X (M8, M16 then annually)        | X  | X                    | X   |                              |
| HbA1c   |                                      | X  |        |              |         | X        | X k                   | X  | X                    | X   |                              |
| Chemistry, hematology, eGFR l                | X i                       | X  | X      | X            | X       | X        | X                                | X  | X                    | X   | X                            |
| Lipids  |                                      | X  |        |              |         | X        |                                  | X  | X                    | X   |                              |
| Pregnancy (WOCBP) m                          | X                                    | X  |        |              | X       | X        | X                                | X  | X                    | X   |                              |
| Urinalysis n                                 | X                                    |  | X      | X            |         |          |                                  | X  | X                    | X   |                              |
| Digoxin level (if applicable) o              | X                                    |  |        | X            |         |          |                                  |  |                      |   |                              |
|   |                                      |  |        |              |         |          |                                  |  |                      |   |                              |

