In Study LX4211.1 202 DM (40) sotagliflozin induced a dose-dependent increase of hematocrit, albumin, and hemoglobin. The mean change (standard deviation [SD]) in hematocrit from Baseline to Week 12 was 0.9% (2.52), 2.0% (2.47), and 1.9% (2.78) in patients receiving sotagliflozin 200 mg qd, 200 mg bid and 400 mg qd, respectively versus -0.5 (2.98) % in the placebo arm. The mean change (SD) in albumin from Baseline to Week 12 was 0.0 (0.279), 0.09 (0.243) and 0.12 (0.242) g/dL in patients receiving sotagliflozin 200 mg qd, 200 mg bid and 400 mg qd, respectively versus (0.273) -0.04 g/dL in the placebo arm. The mean change (SD) in hemoglobin from Baseline to Week 12 was 0.29 (0.775), 0.55 (0.688) and 0.60 (0.820) g/dL in patients receiving sotagliflozin 200 mg qd, 200 mg bid and 400 mg qd, respectively versus -0.19 (1.084) g/dL in the placebo arm. In addition, in the same study, a prespecified sub-analysis of patients with a Baseline BP  $\geq$ 130 mmHg showed that systolic BP decreased by 7 and 14 mmHg (placebo-subtracted), respectively, in the 200 mg qd and 400 mg qd groups.

Therefore, given the observed higher efficacy of the 400 mg dose on glycemic control, hemoconcentration, and BP reduction, and given the potential benefit of these changes on cardiovascular outcomes, the dose of 400 mg was chosen as the proposed maintenance dose for the study.

Sotagliflozin induces an acute, but modest, decrease in estimated glomerular filtration rate (eGFR). Since the study population includes patients at increased risk of acute kidney injury (ie, patients with moderately impaired renal function), study treatment will begin with the low dose of sotagliflozin (200 mg qd) and will be increased to the maintenance dose of 400 mg qd, once tolerability of the low dose has been established by the Investigator.

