Closeout Visit will be the final study visit and no further visits are planned. Study Closeout Visit procedures will differ for patients who do not prematurely permanently discontinue IMP and those who do prematurely permanently discontinue IMP (see [Section 10.1.4.1](#) and [Section 10.1.4.2](#), respectively).

This is an event-driven study. The study will end when approximately 947 primary events have been positively adjudicated (ie, number of patients with at least 1 positively adjudicated primary event) in patients with LVEF <50%, AND approximately 1341 primary events have been positively adjudicated (ie, number of patients with at least 1 positively adjudicated primary event) in the total patient population. All randomized patients will be asked to return to the study site for a Study Closeout Visit once the date the required number of events are projected to be positively adjudicated has been determined. The timing and window of this visit will be communicated to sites.

All patients will continue to be followed after a CV or renal endpoint occurs. Patients with a suspected renal event (reduction of eGFR) should be brought in for an unscheduled visit and have a repeat assessment of renal function 30 to 45 days following the onset of the event to confirm it is sustained (this repeat renal assessment may occur beyond the last planned visit per protocol). If acute renal failure is suspected, further clinical evaluation should be performed as per local standard of care, including confirmation of renal laboratory parameters, and consideration should be given to a nephrology referral (see [Appendix E](#)). Patients will continue with IMP treatment after a CV or renal endpoint occurs unless the criteria for permanent treatment discontinuation have otherwise been met (see [Section 10.3.3](#)).

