### **9.1.2.1 Estimated glomerular filtration rate and dialysis**

Serum creatinine will be assessed as part of serum clinical chemistry at all on-site visits by central laboratory. Estimated glomerular filtration rate will be calculated by the central laboratory using the MDRD equation. The Baseline eGFR value for each patient is defined as the value assessed by the central laboratory at Randomization.

Patients with a suspected renal event (reduction of eGFR) should have a repeat assessment of renal function 30 to 45 days following the onset of the event to confirm it is sustained (this repeat renal assessment may occur beyond the last planned visit per protocol). If acute renal failure is suspected, further clinical evaluation should be performed as per local standard of care, including confirmation of renal laboratory parameters, and consideration should be given to a nephrology referral (see [Appendix E](#)).

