### **9.2.1 Adverse events**

Adverse events including AEs leading to premature treatment discontinuation, SAEs, AESIs, and EOSIs will be assessed. Refer to [Section 10.4](#) to [Section 10.7](#) for details.

All AEs will be collected starting from signing informed consent. The Investigator should take appropriate measures to follow all AEs until clinical recovery is complete and laboratory results have returned to normal, or until stabilization, or until death, in order to ensure the safety of the patients. This may imply that observations will continue beyond the last planned visit per protocol, and that additional investigations may be requested by the monitoring team up to as noticed by the Sponsor.

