### **10.3.3 List of criteria for permanent treatment discontinuation**

The patients may withdraw from treatment with the IMP if they decide to do so, at any time and irrespective of the reason, or this may be the Investigator's decision. All efforts should be made to document the reason(s) for treatment discontinuation and this should be documented in the e-CRF.

Patients who report a CV or renal endpoint as described in [Section 10.4.1.4](#) should remain on IMP until the end of the study, unless there is a safety concern.

The following reasons shall lead to permanent IMP discontinuation:

- At the patient's own request (ie, withdrawal of consent for treatment) (note that this is regardless of whether or not the patient continues in the study)
- If, in the Investigator's opinion, continuation with the administration of the study treatment would be detrimental to the patient's well-being
- Pregnancy (in female patients)
- Any code breaking requested by the Investigator
- Specific request of the Sponsor
- Patient requires dialysis or renal transplantation

- Estimated glomerular filtration  $<15 \text{ mL/min/1.73 m}^2$

**Note:** the central laboratory will alert the Investigator for eGFR values  $<15 \text{ mL/min/1.73 m}^2$ . A repeat determination should be performed within 2 weeks, and study treatment discontinued if the repeat eGFR is  $<15 \text{ mL/min/1.73 m}^2$  (unless a reversible cause is identified [eg, short-term illness or transient volume depletion], in which case an additional repeat determination can be performed after resolution of the short-term illness).

Any abnormal laboratory value or ECG parameter will be immediately rechecked for confirmation before making a decision of permanent discontinuation of the IMP for the concerned patient.

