#### **10.4.6 Guidelines for management of specific laboratory abnormalities**

Decision trees for the management of certain laboratory abnormalities by Sanofi are provided in [Appendix D](#). The study population will be enrolled with preexisting impairment of renal function; rapid change in renal function of greater than **30% as compared** with the **mean of the prior 2 study visits** should be followed up as described in [Appendix E](#).

The following laboratory abnormalities should be monitored, documented, and managed according to the related flow chart in protocol appendices:

- Neutropenia
- Thrombocytopenia
- Increase in ALT
- Increase in creatine phosphokinase suspected to be of non-cardiac origin and not related to intensive physical activity
- Acute worsening of renal function (see [Appendix E](#))

In the event that the 'general guidance for the follow-up of laboratory abnormalities by Sanofi' [Appendix D](#) requires discontinuation of IMP, temporary discontinuation should be considered unless otherwise specified (please see [Section 10.3.1](#)).

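### After a worsening of more than 30% in renal function, Appendix E advises the 1-week recheck only when a cause is found; an unexplained fall has no dated triggered repeat before day 30

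*Protocol*

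**What the plan says.** Protocol Section 10.4.6 states that a "rapid change in renal function of greater than" 30%, measured against the mean of the previous two study visits, is to be followed up under Appendix E. It sets no timing of its own.

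Appendix E has the Investigator look for medications that alter creatinine (an open list of examples) and for six conditions, including volume depletion or expansion and new or worsening heart failure. Its third bullet then reads: "If any of the above conditions are met, the Investigator should take corrective measures to resolve and schedule an interim visit". That visit checks creatinine/GFR and clinical status, and its one-week clock starts with the corrective measures. No branch covers a change for which nothing on the lists is found.

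The other dated step is the confirmation repeat. Section 9.1.2.1 says "Patients with a suspected renal event (reduction of eGFR) should have a repeat assessment of renal function 30 to 45 days" after onset, to show that the fall is sustained; Section 10.1.2 and Appendix E say the same. Section 6.1.2 says such patients "should be brought in for an unscheduled visit and have a repeat assessment of renal function 30 to 45 days" after onset, with no separate date for the unscheduled visit. None of these places gives a numerical threshold for a suspected renal event.

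Only an eGFR below 15 has its own early repeat, in Section 10.3.3: "A repeat determination should be performed within 2 weeks".

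**The concern.** A fall with a cause that has been found and corrected is rechecked at one week. A fall of the same size with no cause found can wait until day 30 to 45 for its first dated triggered recheck. For safety one would expect the unexplained fall to be seen at least as soon.

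Section 4.4.1 gives the reason to care. It says that sotagliflozin produces an acute, modest drop in eGFR and that "the study population includes patients at increased risk of acute kidney injury". Study drug is not itself among the causes listed in Appendix E, so it remains a plausible contributor once the listed causes are ruled out. An early repeat would also inform the choice, raised in the last bullet of Appendix E, of whether to withhold study drug temporarily.

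What is at stake is patient safety. The point changes no endpoint definition, power or alpha.

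**Working it through.** The plan has no figure of its own to reproduce here. The check sets the provisions side by side and takes differences between visit days.

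**1. Which provisions give an early, dated recheck when no cause is found and eGFR is not below 15?**

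| Provision | Depends on a cause? | Timing |
|---|---|---|
| Appendix E interim visit | Yes | 1 week from corrective measures |
| Repeat for a suspected renal event (Sections 6.1.2, 9.1.2.1, 10.1.2; Appendix E) | No | 30 to 45 days from onset |
| Unscheduled visit (Section 6.1.2) | No | No separate day count |
| Acute renal failure branch (Appendix E) | No | Local standard of care, no day count |
| Investigator judgment on renal function (Section 8.8.2) | No | No day count |
| Adverse event follow-up (Section 9.2.1), to "follow all AEs until clinical recovery is complete and laboratory results have returned to normal" or stabilization or death | No | No day count |
| Recheck of any abnormal value (Section 10.3.3) | No | Immediate, but only before a permanent discontinuation decision |
| eGFR below 15 (Section 10.3.3) | No | Within 2 weeks |

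The 30 to 45 day repeat is the only dated, event-triggered step left for the unexplained fall.

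**2. Does the eGFR-below-15 rule cover it?** A fall of just over 30% ends below 15 only if the two-visit mean is below 15 / 0.70 = 21.4. Exclusion E 25 bars patients with a Screening eGFR below 30. From 30, reaching 15 takes a fall of 1 − 15/30 = 50%. So this rule does not reach most falls that meet the trigger.

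**3. When does scheduled chemistry re-measure the patient?** The flow chart row "Chemistry, hematology, eGFR" covers all on-site visits. Target days are 8, 15 and 29 (each ±3) and 113 (±7), then every 4 months.

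- Visit 3 to Visit 4: 15 − 8 = 7 days; at most 18 − 5 = 13 with windows.
- Visit 4 to Visit 5: 29 − 15 = 14 days; at most 32 − 12 = 20 with windows.
- Visit 5 to Visit 6: 113 − 29 = 84 days; 106 − 32 = 74 to 120 − 26 = 94 with windows.
- After Visit 6: about 4 months.

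Falls first seen at Visit 3 or 4 are therefore re-measured before day 30 after onset by the schedule alone. From Visit 5 on, the 30 to 45 day repeat comes before the next scheduled chemistry.

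**4. What would an unconditional one-week visit gain?** Turnaround time is not stated. Assume that the result arrives 0 to 3 days after the sample and that onset is the sample date.

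- First recheck: day 7 + 0 = 7 to day 7 + 3 = 10.
- Smallest gain against the 30 to 45 day repeat: 30 − 10 = 20 days.
- Largest gain: 45 − 7 = 38 days.

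**The case against.** The best reply is that the unexplained case is narrow and already has direction. The Appendix E list is broad: its medication examples are open-ended, and it includes volume shifts, blood pressure changes from diuretic or antihypertensive adjustment, and heart failure exacerbation. In patients just treated for decompensated heart failure and prescribed a loop diuretic, a cause may often be found. If acute renal failure is suspected, Appendix E already asks for laboratory confirmation without requiring a cause. The appendix is guidance, and a careful Investigator would probably retest sooner. All of this stands and limits the importance of the point, but none of it supplies a date.

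Three stronger readings are tempting and not supported:

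- **Every unexplained fall goes unmeasured for weeks.** Scheduled chemistry is close after Visits 3 and 4, and the prior week's creatinine is reviewed at Visit 4 before up-titration.
- **The patient may wait until the next scheduled visit, 74 to 94 days after Visit 5 or about 4 months later on.** That requires an Investigator to treat a fall of more than 30% as something other than a suspected renal event. The term has no threshold, but its only gloss is a reduction of eGFR, and Appendix E repeats the 30 to 45 day rule within its guidance on the 30% trigger. The larger gap should not be claimed.
- **Only an eGFR below 15 is ever rechecked early.** Section 10.3.3 also has an immediate recheck of any abnormal value, though only before a permanent discontinuation decision.

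**Conclusion.** The point holds in limited form. For a worsening of more than 30% with no cause found and eGFR not below 15, the protocol offers no dated, event-triggered recheck before day 30, while an explained and corrected fall is advised to have one at a week. The gap is of practical interest mainly from Visit 5 onward. Closing it gains about 20 to 38 days, given a result delay of 0 to 3 days and onset on the sample date.

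Its overall weight depends on how often unexplained falls occur, which the documents do not report. It is a worthwhile, inexpensive safety improvement rather than a critical flaw. SAP Section 1.1 records that enrollment and follow-up were terminated early, so this is a judgment on the protocol as written.

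**What to change.** Reword the third bullet of Appendix E so that the interim visit is advised for every eGFR decrease that meets the 30% trigger, for example:

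> For each decrease in eGFR meeting this trigger, arrange an interim visit with serum creatinine, eGFR and clinical review. Hold it one week after corrective measures begin if a listed medication or condition is present, or one week after the result is received if none is.

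The text should say decrease rather than change. The present trigger has no direction, and an unconditional rule would otherwise also call in patients whose function improved. Keep the 30 to 45 day repeat as it is, since it serves to confirm a sustained fall.

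The cost is one sentence, plus one extra visit and one creatinine test per unexplained fall. The protocol already uses an early repeat that does not depend on a cause for eGFR below 15, so the approach is not new to it.
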